#### Primary objective:

(1) To evaluate the effectiveness of the intervention in improving parenting among participating caregivers in a fully-powered trial in South Sudan. Taking place in a country outside the Middle East, this will also work to validate the intervention in an additional setting beyond the Middle Eastern context, a crucial step in scaling up BeThere to be a globally-relevant intervention.

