#### Trial design

#### Design

This study is a two-armed, parallel group randomized controlled trial, with an intent to treat design, a 1:1 allocation ratio, and a waitlist control comparison condition. The study will involve Dinka-speaking primary caregivers of children aged 3–14 and a subsample of their children aged 7–14 in five communities in Bor County, Jonglei State, South Sudan: Pariak, Ghoi, Taragok, Tibek, and Lenguet. Random allocation to intervention and control arms will be done at the family level to ensure caregivers from the same family do not participate in different arms of the study.

We will evaluate the effectiveness of BeThere—a nine-week preventative group psychosocial support intervention for primary caregivers of children aged 3-14-by measuring multiple parenting and psychosocial outcomes among participating caregivers compared to a waitlist control group of caregivers not participating in a parenting intervention. Quantitative data collection will be done by trained research assistants (RAs) using electronic tablets at four timepoints: baseline, midline, endline, and three-month follow up. Prior to the start of data collection, all research instruments will go through a process of translation, adaptation, cognitive interviewing, and pilot testing. The primary outcome of the study will be an overall score on parenting. Secondary outcomes will be child wellbeing (caregiver- and childreported), caregiver stress, distress, and wellbeing, as well as harsh parenting and parental warmth and responsiveness. Additionally, demographics data will be collected from caregivers and children. We will also record participant attendance to intervention sessions, along with facilitator competence to deliver the intervention and their fidelity in delivering the intervention as planned. Additional qualitative data will be gathered via focus group discussions and key informant interviews. The study will be conducted between January and July 2025.

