#### Primary outcome measures

#### **Parenting**

Parenting will be assessed using a 24-item parenting scale developed to assess change in parenting in the development and testing of BeThere (Miller et al., 2024). In addition to yielding a total score, the measure includes subscales assessing parental warmth and sensitivity (16 items) and harsh parenting (five items). Internal consistency for the full measure ( $\alpha$  = 0.83) and the parental warmth ( $\alpha$  =0.86) subscale was good in the previous RCT, and was acceptable for the harsh parenting subscale ( $\alpha$  = 0.76). The measure was designed as a parent-reported measure, but for this study we will also develop a child-reported version to give us data on parenting from both caregivers and children. The overall parenting score will be considered a primary outcome, while the two subscales will be secondary outcomes.

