#### Child psychosocial wellbeing

Children's psychosocial wellbeing will be assessed with the Kiddy-KINDL for Parents for index children aged 3–6 years and the Kid-KINDL for Parents for index children aged 7–12 (Ravens-Sieberer & Bullinger, 1998). The four school items will be dropped to make the two versions identical, and four optional mental health items will be added to strengthen our measure of children's psychosocial health. Additionally, as we are looking to measure changes in parenting at the caregiver level, we will split up item 13 (*my child got on well with us as parents*) into two items to ask about both caregivers separately where applicable. This will yield a total of 25 items. All the items will be worded as questions rather than statements to enhance their understandability. Self-reported psychosocial wellbeing of the index children aged 7–14 will be assessed using the Kid-KINDL for Children which will have the same adaptations as the caregiver-version, allowing us to compare the child- and caregiver-reported versions. Internal consistency of the parent-completed KINDL in the previous RCT was good across measurement points ( $\alpha$ =0.86–0.91; Jordans et al., 2023).

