#### **Analyses**

The statistical analyses will be carried out by the trial statistician, who will remain masked to the group randomization until the main analyses are complete. The analyses outlined in this strategy will be primarily based on an intention to treat; a per protocol analysis will be the secondary analysis. The per protocol analysis will include participants who complete the intervention, with completion defined as attending at least seven of the nine sessions, and will exclude any participant who attended fewer than seven sessions. We have powered the study (see the "Sample size" section) as a superiority study at 10 weeks. The first stage of analyses will be a descriptive model of the data to assess completeness of data and the integrity of the data collection system. Participants and area characteristics and demographics will be summarized at baseline. Clinical characteristics that have been measured repeatedly will be summarized at baseline and at the post-randomization follow-up assessments. In addition, patterns of missing data will be described.

The primary outcomes (total score of parenting scale and proxy-reported child psychosocial wellbeing) will be analyzed using linear mixed models to model the mean difference in the total score of parenting scale 10 weeks post-randomization. The linear mixed models will be adjusted for baseline total scores and stratification. A two-level hierarchical model will be employed to improve power and take into account clustering of the parents at the family level. These models utilize maximum likelihood estimation and thus allow for missing outcome data under the missing at random assumption. Associations between post-randomization variables and missingness will be dealt with by multiple imputation, again

under the missing at random assumption. Departures from this assumption will be assessed with a sensitivity analysis. Secondary outcomes, including parental warmth and responsiveness, harsh parenting, caregiver psychosocial wellbeing, stress, and distress, and self-reported child psychosocial wellbeing will be assessed with a similar methodology used for the primary outcomes, using generalized linear mixed models depending on the type of outcome (normal, ordinal).

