#### Full structural model

For the post-intervention showing a significant intervention effect on children's psychosocial wellbeing, a parametric structural equation modelling approach, which is a statistical technique to test different pathways of the intervention effect on children's psychosocial

wellbeing (Structural Equation Modeling package in Stata version 18.0) will be used. We will estimate the total effect: the natural indirect effects (NIE), and natural direct effects (NDE) of BeThere on child psychosocial wellbeing for; (i) caregiver's scores (primary) and (ii) caregiver's scores (secondary) on Caregiver Distress, Caregiver Psychosocial Wellbeing and Harsh Parenting. The NDE represented the effect of BeThere on Child Psychosocial Wellbeing-parent report that was independent of Caregiver Psychological Distress, Caregiver Psychosocial Wellbeing, Caregiver Harsh Parenting. Caregiver Stress and Caregiver Stress Management. An NIE represented the proportion of BeThere that could be explained by its effect with changes in Caregiver Psychological Distress, Caregiver Psychosocial Wellbeing, Caregiver Harsh Parenting. Caregiver stress and Caregiver Stress management. To quantify the magnitude of mediation, the study will estimate the proportion of the effect mediated by Caregiver Psychological Distress, Caregiver Psychosocial Wellbeing, Caregiver Harsh Parenting., Caregiver stress and Caregiver Stress management (NIE/[NDE + NIE]). All analyses will be estimated using bootstrapping (500 replications) to recover the correct SEs for direct and indirect effects Results are presented as coefficients and 95 % confidence intervals from linear regression. Statistical significance was set a priori at p < 0.05 with no adjustment for multiplicity. Primary mediation analyses will be conducted using data from female caregivers, and secondary mediation analysis using combined data from male and female caregivers for each one of the multiple mediators.

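### The Analyses section makes proxy-reported child wellbeing a second primary outcome, although the design, the primary objective and the outcome listing make it secondary

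*Protocol*

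**What the plan says.** Five places in the protocol bear on which outcome is primary.

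- **Objectives, Primary objective** (also in the Study Synopsis): "To evaluate the effectiveness of the intervention in improving parenting among participating caregivers in a fully-powered trial in South Sudan". Child outcomes appear only in the secondary objectives.
- **Trial design, Design**: "The primary outcome of the study will be an overall score on parenting". The next sentence reads "Secondary outcomes will be child wellbeing (caregiver- and childreported), caregiver stress, distress, and wellbeing", so both the caregiver report and the child report of wellbeing are secondary.
- **Primary outcome measures, Parenting**: "The overall parenting score will be considered a primary outcome, while the two subscales will be secondary outcomes". No other instrument is described under this heading.
- **Secondary outcome measures, Child psychosocial wellbeing**: "Children's psychosocial wellbeing will be assessed with the Kiddy-KINDL for Parents for index children aged 3–6 years". The parent-completed instrument is therefore placed among the secondary measures.
- **Statistics, Analyses**: "The primary outcomes (total score of parenting scale and proxy-reported child psychosocial wellbeing) will be analyzed using linear mixed models". The secondary list in the same section keeps only the self-reported version of child wellbeing.

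The Analyses sentence goes on to define the model's target as the between-arm mean difference in the parenting total 10 weeks after randomization. It gives no corresponding target for child wellbeing.

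**The concern.** A protocol has to fix which outcome carries the confirmatory claim. It cannot leave this to a later analysis plan, because a plan that follows one section here would contradict another. The Analyses wording is also consistent within itself (proxy report primary, self-report secondary), so a reader who sees only that section would have no reason to suspect a slip.

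The choice could matter for the conclusion. Under Research to date, the protocol describes the previous trial as showing slightly better parenting outcomes, and an effect on caregiver-reported child wellbeing at endline that was gone at three months. It is quite possible that one of these outcomes is positive in the new trial and the other is not. A report could then say that the primary outcome was met, or that it was not, and cite the protocol for either statement. The protocol's Trial Registration section gives preventing selective reporting as a purpose of registration, and this ambiguity works against that purpose.

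**Working it through.** **Step 1. Compare the sections.** Proxy-reported in Analyses and caregiver-reported in Design mean the same thing: the parent version of the KINDL.

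| Section | Parenting total | Caregiver-reported child wellbeing | Child-reported wellbeing |
|---|---|---|---|
| Primary objective | subject of the objective | not mentioned | not mentioned |
| Design | primary (singular, definite) | secondary | secondary |
| Outcomes | under the primary heading | under the secondary heading | under the secondary heading |
| Analyses, outcome labels | primary | **primary** | secondary |
| Analyses, stated model target | yes, at 10 weeks | none | none |

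Only the label in Analyses departs from the rest. The conflict with Design is direct, because the same measure is called secondary in one place and primary in the other.

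**Step 2. Is there a figure to reproduce?** No. The protocol states no error rate for the primary outcomes taken together. Its only computed design figure, 425 caregivers per group, concerns an indirect effect in the mediation analysis and does not bear on this point.

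**Step 3. What would follow if either outcome sufficed?** The inputs are two tests at two-sided 0.05 each. The protocol uses that level in its mediation sample-size calculation; the Analyses section states no level for the primary tests, so it is an assumption here. The correlation r between the two test statistics is not given and is varied.

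For independent tests:

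1 − (1 − 0.05)² = 1 − 0.9025 = 0.0975

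For correlated tests, with (Z₁, Z₂) standard bivariate normal with correlation r:

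1 − P(|Z₁| ≤ 1.96 and |Z₂| ≤ 1.96)

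| Assumed r | Chance of at least one false positive |
|---|---|
| 0 | 0.0975 |
| 0.2 | 0.0964 |
| 0.5 | 0.0907 |
| 0.7 | 0.0835 |
| 0.9 | 0.0704 |
| one primary outcome | 0.05 |

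**Step 4. Other decision rules.**

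- *Both outcomes required.* The error rate for the joint claim does not exceed 0.05. The power of the joint claim cannot exceed the lower of the two individual powers.
- *Fixed order, parenting first.* Child wellbeing is tested only if parenting is significant. The overall error stays at 0.05 and parenting keeps its full level.
- *Equal split, 0.025 each.* The overall error if independent is 1 − 0.975² = 0.0494. A test with an assumed 80% power at 0.05 falls to Φ(1.960 + 0.842 − 2.241) = Φ(0.560) = 71.2%. Restoring 80% needs ((2.241 + 0.842)/(1.960 + 0.842))² = 1.21 times the sample, or about 21% more participants. For an assumed 90% power, the fall is to 84.1% and the increase is about 18%.

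**The case against.** The strongest defence is that the intended reading is clear. The objective, the Design section and the placement of the KINDL all point to parenting alone. The Analyses sentence itself gives a model target only for the parenting score, which suggests that its parenthesis is a drafting slip. This stands as evidence of what was probably meant, but it does not remove the contradiction: the parenthesis and the matching secondary list are in force as written.

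A reader might go further and infer that the trial is set up to claim success on either outcome at an unadjusted 5%. The documents do not support that. No section says that one positive outcome suffices. Two outcomes called primary could equally mean that both are required or that they are tested in order, and an analysis plan not shown here may settle this. Nor does the sentence "Statistical significance was set a priori at p < 0.05 with no adjustment for multiplicity" supply the missing rule. It stands in the Full structural model section, among the bootstrapped direct and indirect effects, and concerns the mediation analyses. It is not evidence about the primary comparison.

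Two further limits hold. The Parenting section calls the score only a primary outcome, under a plural heading, so it does not by itself exclude a second; the explicit conflict is with Design. And independence is the least favourable case in the table above and an unlikely one, since the same caregiver rates both scales with reference to the same index child.

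**Conclusion.** The point holds as a contradiction over the status of caregiver-reported child wellbeing, and it must be fixed on that ground alone. As written, the protocol can be cited for two different answers to whether the primary outcome was met.

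The error inflation is conditional. It would be 9.75% under independence and 7.0% at an assumed correlation of 0.9, against 5% for one primary outcome. This applies only if success on either outcome, each at two-sided 0.05, were taken as success, which the protocol neither states nor excludes. If both outcomes were required, or if they were tested in a fixed order, there would be no inflation.

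**What to change.** In Statistics, Analyses, name the caregiver-reported total parenting score at 10 weeks as the sole primary outcome, and add proxy-reported child psychosocial wellbeing to the secondary list beside the self-reported version. This brings the section into line with the objective, the Design section and the outcome listing. It is an edit to that section only and needs no new data and no change in sample size. It should be made and dated before anyone sees outcomes by arm.

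If the sponsor does want two primary outcomes, the change is larger. The primary objective (in both the Synopsis and Objectives), the Design section, the primary and secondary outcome listings and the Analyses section must all say so. Analyses must also give a model target for child wellbeing and state a decision rule. Testing parenting first, and child wellbeing only if parenting is significant, keeps parenting at the full 0.05. Splitting the level would cost the power shown above. Power for the second outcome would also need support, because the sample-size section calculates power only for an indirect effect.

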#### **Exclusion** criteria

- Under 18 years of age
- Participation by either caregiver in a parenting or stress management intervention in the past six months
- Family does not have a child aged 3–14 years

- Anyone who is unable, even with assistance, to complete the assessment questionnaires
- Unwillingness of either caregiver to give informed consent
- Not fluent in Dinka

Based on the successful implementation of the design in the pilot RCT and RCT in Lebanon, a waitlist control will serve as the comparison group in this study. Participants in the waitlist control group will be given the opportunity to participate in the intervention after the 3-month follow-up assessment has been completed.

This study will involve a waitlist control group for two key reasons:

- 1) While the risk of a nocebo effect among research participants randomized into the control group in waitlist-controlled psychological treatment trials has been raised (Furukawa et al., 2014; Gold et al., 2017; Steinert et al., 2017), there is currently little evidence to show that this is the case for preventative interventions (Gold et al., 2017; Miller, et al., 2023).
- 2) The BeThere intervention has already been shown to be effective among caregivers in Lebanon. Considering the vulnerability of the target population and the lack of existing mental health and psychosocial support services, we do not want to deny control group participants access to the intervention.

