#### **Facilitators**

20 facilitators will be recruited to implement a total of 80 intervention groups, 40 in each arm of the trial. BeThere facilitators must fulfil the following criteria to be accepted into the facilitator training:

- 1) Fluent Dinka speaker
- 2) Preferably from the geographic locations of implementation
- 3) Aged at least 24 years
- 4) At least high school education completed
- 5) At least 2 years of experience implementing psychosocial interventions, preferably with adults, especially parents and caregivers
- 6) Affinity with the core ideas of the intervention regarding parental wellbeing and positive parenting
- 7) Able to commit to attend the full training, all sessions of the intervention, and all supervision meetings
- 8) Respectful and tolerant to different nationalities and religious groups
- 9) Being a parent is highly desirable but not required

Prospective BeThere facilitators will participate in a 6-day training that covers the intervention material as well as key group facilitation skills and competencies. The competency of the trainees will be assessed with standardized competency measurement

<sup>3 While being a parent introduces the risk of bias as facilitators may introduce their own experiences and attitudes about parenting, we have found that intervention participants view facilitators with children as having greater legitimacy to lead sessions on parenting knowledge and skills; in addition, facilitator-parents may have a deeper appreciation for the challenges and stressors that parents face. We make every effort, in training, supervision, and on-site coaching, to ensure that any bias introduced to the sessions by facilitators, whether due to having children or any other source, is minimized.

tools. We will purposefully include more facilitators than we need in the training, with final selection of facilitators taking placed afterwards based on performance in the training. This will also ensure we have individuals who have been trained in the intervention as backup in the case of facilitator dropouts. The 6-day training will be followed by a practice run of the full 9-session intervention, during which the facilitators will receive close support and supervision from trained BeThere supervisors.

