#### Intervention

BeThere (Miller et al., 2020) is a nine-session weekly group intervention, co-facilitated by trained non-mental health professionals, who receive 6 days of training, three on-site observations with feedback, and weekly supervision. Groups are offered separately to women and men and are run with 10-12 participants. Table 1 above lists session topics and corresponding modules, along with the stress management technique(s) taught in each session. Sessions 1-4 are focused on strengthening caregiver wellbeing, with individual sessions on understanding and managing stress, disengaging from rumination, and coping with anger and frustration, all while developing the group as a socially supportive setting. Sessions 5–8 focus on strengthening parenting under conditions of adversity (i.e., increasing awareness of the impact of stress on parenting, increasing positive parent-child interactions and the use of non-violent discipline methods, and reducing harsh parenting). Session 9 involves a review and closing of the intervention. In all but the final session, participants learn a new relaxation or stress management technique, drawn or adapted from the mindfulness and stress management practice. These techniques are also provided to participants in Dinka on mp3 files, which they can listen to on their smart phones or on mp3 players provided at the start of the program. Participants are encouraged to practice these activities at least three times each week. A considerable amount of time is spent at the start of each session reviewing the home practice and collectively problem-solving any barriers to practicing the techniques.

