#### **Methods**

#### Randomization

960 caregivers will be randomized into the two arms. After caregivers have completed the baseline assessment, families will be randomized to the BeThere intervention or a waitlist control group. Randomization will be at the family level to ensure that caregivers from the same family are not randomized into different arms of the study. BeThere groups will be held separately for women and men, yielding a total of 480 caregivers per arm. As we are running the study in five communities, a block randomization design will be used: the total sample (n=960) will be divided equally across the five communities, resulting in a sample of 192 caregivers per community, randomly allocated to either the experimental or control arm (n=96 per arm). They will then be organized into eight intervention groups of approximately 12 caregivers per group in each arm.

[figure not shown]

Figure 5 Randomization and allocation flowchart

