#### **Statistics**

#### Power and sample size

To gain a general appreciation for the required sample size to detect an indirect effect through the primary mediators (Caregiver Distress, Wellbeing, and Harsh Parenting), we used the sample size estimator for joint significance indirect effects developed by Vittinghoff and Neilands (2015). With a two-sided alpha of 0.05, for an intervention-mediator error term correlation coefficient of 0.2, a standard deviation of the mediator of 0.2, and a standard deviation of the random error term of 0.5, a sample of 425 caregivers per group would be sufficient to detect a mean difference of 0.4 (Vittinghoff & Neilands, 2015). All parameter estimates are based on our previous work. Sample size estimators for multiple mediator models are currently unavailable (VanderWeele, 2016); however, O'Rourke and Mackinnon (2015) provide evidence that multiple mediator models have more power than single mediator models. Thus, we expect this study to have sufficient power for multiple mediator models. With a 10% attrition we expect to have 468 families per group with 234 children, totaling 936 caregivers and 468 children. With a total of 40 intervention groups, the final sample size is 960 caregivers (equivalent of 480 families or more) and 400 index children.

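### The primary model clusters by family only, so if outcomes are correlated within BeThere delivery groups its standard errors are too small

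*Protocol*

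**What the plan says.** The Analyses section of the Protocol names one level of clustering for the primary outcome: "A two-level hierarchical model will be employed to improve power and take into account clustering of the parents at the family level". The other terms are also fixed: "The linear mixed models will be adjusted for baseline total scores and stratification". Secondary outcomes follow a similar method. Nowhere is a term for delivery group or facilitator added.

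Delivery is described in three places. Facilitators: "20 facilitators will be recruited to implement a total of 80 intervention groups, 40 in each arm of the trial". Randomization: "They will then be organized into eight intervention groups of approximately 12 caregivers per group in each arm". Intervention: "Groups are offered separately to women and men and are run with 10-12 participants". The timing for the control arm stands under Exclusion criteria: "Participants in the waitlist control group will be given the opportunity to participate in the intervention after the 3-month follow-up assessment has been completed".

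The Power and sample size section uses the 40 groups to reach 960 caregivers, but states no ICC and no design effect.

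**The concern.** Caregivers in one BeThere group share members, facilitators and nine weeks of sessions. The Intervention section describes the group as a source of social support, and the fourth objective and the mediation plan treat cohesion as a possible mechanism. On the protocol's own reasoning, outcomes may therefore be correlated within a group.

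The stated model has no place for that correlation:

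- **Family term.** Men and women meet separately, so two caregivers of one family attend different groups. Family and group are crossed.
- **Community term.** Taking stratification to mean community, each community has eight intervention-arm groups, so a community effect cannot stand in for them.
- **One arm only.** No waitlist group meets before the 3-month follow-up, so at the 10-week endpoint the correlation can arise only in the intervention arm.

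At stake are the size of the primary test and the coverage of its confidence interval, and the same for the caregiver-level secondary outcomes.

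**Working it through.** **Inputs from the Protocol.** Allocation: "a 1:1 allocation ratio" (Design), with 480 caregivers per arm (Randomization). Groups: 40 in the intervention arm, about 12 in each. Level: "With a two-sided alpha of 0.05" (Power and sample size). That level is given for the mediation calculation; I assume it also applies to the primary test.

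**Assumptions.** The group ICC is varied from 0 to 0.10 and the family ICC from 0 to 0.4, since the protocol gives neither. All families have two caregivers (240 families per arm). Single-caregiver families would move results towards the family ICC 0 column below.

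**Step 1: the plan's own figure.** 5 communities × 8 groups = 40 groups. 40 × 12 = 480 per arm. 480 × 2 = 960. This reproduces exactly, and no clustering allowance enters it.

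**Step 2: true and model variance.** Scale the variance outside the group component to 1, with family part vf (the family ICC) and residual ve = 1 − vf. For group ICC r, the group variance is vg = r/(1 − r), in the intervention arm only.

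- True variance of the difference: 2(vf/240 + ve/480) + vg/40
- Variance the family-only model estimates: 2(vf/240 + ve/480) + vg/480
- Type I error: 2[1 − Φ(1.96/√ratio)], where ratio is true over model variance

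**Step 3: one case in full (group ICC 0.05, family ICC 0.2).**

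- vg = 0.05/0.95 = 0.0526
- 2(0.2/240 + 0.8/480) = 0.00500
- True: 0.00500 + 0.0526/40 = 0.00632
- Model: 0.00500 + 0.0526/480 = 0.00511
- Ratio 1.236, so the true SE is 1.112 times the model SE
- 1.96/1.112 = 1.763, giving a type I error of 7.8%
- Coverage of the nominal 95% interval: 100 − 7.8 = 92.2%

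**Step 4: the range.**

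| Group ICC | Family ICC 0 | 0.2 | 0.4 | True SE / model SE |
|---|---|---|---|---|
| 0 | 5.0% | 5.0% | 5.0% | 1.00 |
| 0.01 | 5.6% | 5.5% | 5.5% | 1.02–1.03 |
| 0.02 | 6.3% | 6.1% | 5.9% | 1.04–1.05 |
| 0.05 | 8.4% | 7.8% | 7.4% | 1.10–1.13 |
| 0.10 | 11.9% | 10.8% | 10.0% | 1.19–1.26 |

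With 10% attrition (432 per arm) the type I error runs from 5.4% to 11.1% for group ICC 0.01 to 0.10.

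**Step 5: simulation.** 20,000 trials per setting had a zero mean difference, groups crossed with family and community as a fixed effect. At group ICC 0, 0.01, 0.02, 0.05 and 0.10, the rejection rates were 5.1, 5.8, 6.2, 8.5 and 11.8% (family ICC 0) and 5.2, 5.7, 6.0, 7.8 and 10.7% (family ICC 0.3). This agrees with the formula.

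**Step 6: the repaired model.** A random group effect was added in the intervention arm only (family ICC 0.3, REML, normal reference, 1,500 trials per setting). Rejection was 4.6, 4.5 and 5.1% at group ICC 0.02, 0.05 and 0.10. The Monte Carlo standard error is about 0.6 points.

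**Step 7: what honest intervals cost.** At family ICC 0.2 and 80% power, the detectable difference is 2.80 × √(true variance). It is 0.198 SD at group ICC 0, 0.208 at 0.02, 0.223 at 0.05 and 0.247 at 0.10.

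**The case against.** **The size is unknown.** The documents give no group ICC. At 0 the test has its nominal size, and at 0.01 to 0.02 the excess is roughly half a point to just over one point. This stands. A reader might infer from group delivery alone that type I error is known to exceed 5%. The documents do not support that: they make a positive ICC plausible, not certain, and the larger figures rest on assumed ICCs of 0.05 to 0.10.

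**Which null hypothesis?** Families are randomized. If BeThere affected nobody, there would be no group effects of treatment and the family-level test would keep its size. This also stands. The excess belongs to the null of zero average difference with groups varying around it. That is still the hypothesis a mean-difference model tests, and interval coverage suffers in the same way when BeThere works.

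**Direction.** A reader might infer that the intervals are tilted in favour of the intervention. They are not. The estimate is not shifted, and the interval is too short on both sides.

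**Both arms grouped?** The Facilitators and Randomization sections count groups in each arm, so a reader might take both arms as clustered. Waitlist groups do not meet until after the last assessment, so that does not apply at 10 weeks.

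**Leave it to the SAP.** This would answer an open point, but the protocol states the level of clustering itself. A SAP that followed it would carry the gap forward.

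**Practical limits.** A group variable with clusters in one arm and singletons in the other would reveal allocation to a statistician whom the Analyses and Masking sections keep masked. Child self-report also has a different structure. Both objections stand and shape the fix.

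**Conclusion.** The concern holds in conditional form. The primary model omits a level of clustering that the trial's own delivery creates in one arm, and no other term in the model replaces it. If the delivery-group ICC is above zero, standard errors are too small. The type I error for a zero mean difference is then about 5.5% at ICC 0.01, 6% at 0.02, 7.4 to 8.4% at 0.05 and 10 to 12% at 0.10. These figures assume 480 caregivers per arm, equal groups of 12 and family ICCs from 0 to 0.4. Correlation from facilitators who lead several groups is not counted and could add to them.

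This should be fixed before unmasking. It is not a fatal flaw, because the excess is small at low ICCs and the repair is a matter of analysis wording.

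**What to change.** **Caregiver-reported outcomes.** Keep the family random intercept. Add a random effect for BeThere group in the intervention arm only, crossed with family, with each control caregiver as a singleton and community as a fixed stratum. Use the group as assigned, including for caregivers who never attend. The attendance registers may not list those caregivers, so assigned group should be recorded at allocation.

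**Child self-report.** There is one index child per family, so drop the family intercept. A child with two participating caregivers is linked to two groups. Use a multiple-membership group term or a variance estimate robust to group.

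**Masking.** State how it is kept, for example with coded group identifiers in both arms or by having an unmasked person prepare or fit this term.

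**Optional.** Small-sample degrees of freedom and arm-specific residual variances are refinements. The former would require REML in place of the stated maximum likelihood. Neither was needed to bring the simulated error back to about 5%.

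**Cost.** The wording changes, assigned group must be recorded and a masking step is added. Intervals widen modestly: at group ICC 0.05 and family ICC 0.2 the detectable difference grows by about 13% (0.223/0.198). If the group ICC is near zero, little is lost.
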